patients (7 men and 8 women, mean age 62 years) who underwent OctreoScan with SPECT/CT of the chest for a clinical indication between the periods of April and November of 2013 at the University of Washington in Seattle. Most common clinical indication was detection of local and/or metastatic neuroendocrine tumors. Patients were injected with ~ 6 mCi of OctreoScan, and SPECT/CT of the chest was acquired 24 hr post-injection. OctreoScan uptake was semiquantitatively calculated using a target to blood pool ratio approach. Figure 2 depicts fused SPECT/CT images of how this was performed. Circular region of interests (ROI) of ~20 mm diameter were applied to left ventricular (LV) cavity blood pool (used as background, 2A and 2D), LV anterior (2B), inferior (2C), lateral wall (2E) and septum (2F), as well as the lungs (not shown), liver (2G), spleen (2G) and kidneys (2H). Results: Visually, the myocardium exhibited indistinguishable activity compared to the LV blood pool. However, there was significant LV regional differences in the uptake ratio/index as shown in **Table 1**. The inferior wall and septum showed higher (above blood pool) and the lateral and anterior walls lower (below blood pool) uptake ratios. This is most likely due to scatter emitted from the liver and spleen (Fig 2G) into the inferior wall (Fig 2C) and, to a lesser extent, the inferior portion of the septum. Likewise, identification of the septal wall (Fig 2F) was difficult given the lack of enough contrast definition on SPECT and CT images, for which an anatomical assumption was made, which makes ROI-based estimates less accurate at this location. These data demonstrated that under baseline conditions. OctreoScan uptake in the heart is indistinguishable from LV blood pool (~ 0.94 ± 0.17). These findings provide solid empirical basis for the work proposed in this project; the hypotheses are mechanistically plausible, clinically important, and testable.

d. Differences between OctreoScan and DOTATATE

There are important biological, technical, and practical differences between these radiopharmaceuticals that deserve a brief mention. Like indium-111 pentetrotide (Octreoscan®), 68-gallium dotatate has similar affinity for the same group of somatostatin receptors in inflammatory leukocytes (preferentially somatostatin receptor 2). The availability of 68-gallium dotatate provides several advantages, which are highly beneficial to the patients in this pilot study, including:

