Enrolled patients will be prospectively imaged after injection of either the radiotracer Indium-111 Penteotride (OctreoScan) or DOTATATE. We expect imaging 10 patients with OctreoScan and 20 patients with DOTATATE. No one will receive both radiotracer injections.

Patients will be scheduled for imaging Tuesday through Friday (no Mondays), since the dose of OctreoScan and DOTATATE must be requested by noon for next day delivery. Subjects will be advised to remain well hydrated prior to and for at least one day after tracer injection, this to reduce radiation exposure.

Women may participate in this study only if they are certain they are not pregnant. If the subject is a woman of childbearing age, a pregnancy test will be performed before OctreoScan or DOTATATE injection unless she has a history of total hysterectomy, is post-menopausal for more than 2 years or post-tubal ligation for more than 1 year.

OctreoScan Protocol

Visit 1 (Screening)

- Review the study with the subject and obtain written informed consent and HIPAA authorization.
- Assign the subject a unique study number.
- Record demographics data.
- Record medical history, including a history of biopsy-proven systemic sarcoidosis, diagnosis date, and prior treatments.
- Record concomitant medications.
- Schedule subject for Visit 2.

Visit 2 (Study Day 1)

- Subject arrives to the Nuclear Medicine Department.
- Concomitant medications review.
- Perform abbreviated physical examination.
- Perform and record vital signs.
- Place a peripheral intravenous (IV) line.
- Perform STAT quantitative serum hCG testing prior to each administration of Octreoscan
- Administer OctreoScan IV.
- Observe patient for 30 minutes post OctreoScan injection.
- Patient is to have a break and return to the Nuclear Medicine Department in 4 hours.
- Perform first set of images (~90 minutes)
- Subject can leave the Nuclear Medicine Department

[figure not shown]
Visit 3 (Study Day 2)

- Subject returns to the Nuclear Medicine Department 24 hours after OctreoScan injection
- Record any Adverse Experiences.
- Perform second set of images (~90 minutes).
- Subject has completed the study protocol at this point.

Follow Up

• All patients will be contacted by telephone at approximately 36-48 hours following the last scan for AE monitoring.

Figure 3. Example of Study Visits for OctreoScan Protocol

Study Day 1 (Approximately 6 hours)

Study Day 2 (Approximately 2 hours)

24 hours post	Whole Body	SPECT/CT	

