DOTATATE will be given intravenously at the dose of 4.0 mCi (148 MBq). They will then be observed for 60 minutes post DOTATATE injection at the nuclear medicine lab.

Cardiac acquisition: Individuals will be positioned with the help of a CT topogram (grid over the heart, level of the carina), and a low-dose CT scan (120 kVp, 20 - 30 mA) will be acquired for attenuation correction of PET emission data to cover the entire chest. This will be followed by a 20-minute ECG-gated 3-D PET acquisition of the chest and myocardium.

Imaging Processing:

All PET images will be reconstructed with attenuation correction (Matrix 128x128, OSEM, subsets 28, iteration 2, post filter 6.0 mm), and processed and reviewed using the vendor-supplied HERMES software package.

d. Data to be collected and when the data is to be collected

Visit 1. We will collect demographics data, medical history, prior treatments, and concomitant medications, as well as confirm a negative STAT quantitative serum hCG testing prior to the administration of Octreoscan or DOTATATE.

After visit 3 for OctreoScan or after visit 2 for DOTATATE we will analyze and interpret the images as following:

Image Interpretation for OctreoScan:

OctreoScan uptake in the heart will be assessed both qualitative and semi-quantitatively.

1. Qualitative Assessment of OctreoScan cardiac uptake: Two board-certified nuclear medicine physicians will review the early and delayed whole body planar and SPECT/CT images independently of each other and grade each image set based on OctreoScan uptake in the heart as: 1) negative, 2) borderline positive or 3) definitely positive. In this latter case, the number and location (relative to the left ventricular wall position) of positive lesions will be recorded. Similarly, FDG-PET studies (performed as part of the inclusion criteria) will be reviewed and the number and location of FDG-avid lesions recorded.

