Primary Endpoint: Positive or abnormal OctreoScan or DOTATATE uptake in patients with cardiac sarcoidosis

Secondary Endpoint: Differences in OctreoScan uptake at 4 hours vs. 24 hours post-radiotracer injection

c. Statistical methods

Data Ascertainment and Analysis:

All statistical analysis will be done using SPSS (version 21.0). A P value <0.05 will be considered statistically significant for all calculations.

Qualitative assessment of OctreoScan or DOTATATE cardiac uptake: First, Cohen's kappa coefficient will be used to examine the visual inter-rater agreement between readers. We expect a kappa of at least 0.9 (excellent). Subsequently, the percentage of patients with abnormal OctreoScan or DOTATATE will be compared between patients with suspected sarcoidosis and those in a control group (Table 1, Figure 2) using chi2.

Semiquantitative assessment of OctreoScan or DOTATATE cardiac uptake: The heart-to-blood pool ratio is a unitless continuous variable. We will use paired t-test to compare within group OctreoScan uptake between early and delayed imaging, and independent-measures t test to compare OctreoScan or DOTATATE uptake between patients with suspected sarcoidosis and the control group.

We will also investigate whether delayed imaging may lead to improved lesion detection performance due to a higher/better target-to-background ratio compared to early imaging. We will employ chi2 to compare if percentage of patients with abnormal OctreoScan varies significantly both on a patient- and lesion-basis between early and delayed imaging in both study groups.

Evaluation of early vs. delay imaging: We will employ chi2 to compare if percentage of patients with abnormal OctreoScan varies significantly both on a patient- as well as lesion-basis between early and delayed imaging in both study groups.

Comparison with FDG-PET: We will also compare if foci of increased OctreoScan or DOTATATE uptake are similar in number and localization compared to FDG-PET scans.

Expected Results:

Our main hypothesis is that OctreoScan or DOTATATE uptake in the heart will be semiquantitatively (heart-to blood pool ratio will be ≥ 2.0) high enough to allow visualization of OctreoScan or DOTATATE activity in patients with cardiac sarcoidosis, compared to the control group, where myocardial uptake will be similar to blood pool activity (heart-to blood pool ratio of ~ 1.0).

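### Early (4 h) and delayed (24 h) OctreoScan detection rates come from the same roughly 10 patients, but the plan names only chi2, with no paired form, and extends the comparison to a group that has no early images

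*Combined protocol and SAP*

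**What the plan says.** All references are to the combined protocol and SAP.

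- **Size.** Section V.a: "We expect imaging 10 patients with OctreoScan and 20 patients with DOTATATE". Sections V.a and V.c have each OctreoScan patient imaged at 4 h and at 24 h after one injection.
- **Continuous ratio.** Biostatistical Analysis, c. Statistical methods, separates two designs. Within patients: "We will use paired t-test to compare within group OctreoScan uptake between early and delayed imaging". Between groups: "independent-measures t test to compare OctreoScan or DOTATATE uptake between patients with suspected sarcoidosis and the control group".
- **Percentages.** The same section uses the single word chi2 for patients versus controls and, in two places, for early versus delayed imaging. One is "We will employ chi2 to compare if percentage of patients with abnormal OctreoScan varies significantly both on a patient- as well as lesion-basis". The other says the percentage is tested for whether it "varies significantly both on a patient- and lesion-basis between early and delayed imaging in both study groups".
- **Lesions.** Section V.d, Qualitative Assessment, grades each image set as negative, borderline or definitely positive. For definitely positive sets: "In this latter case, the number and location (relative to the left ventricular wall position) of positive lesions will be recorded". For FDG-PET, it has "the number and location of FDG-avid lesions recorded". The statistical text does not say which lesions form the denominator.
- **Controls.** Statistical methods identifies the control group as the Table 1 and Figure 2 series of 15 patients. Section I.c says of that series: "SPECT/CT of the chest was acquired 24 hr post-injection".

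**The concern.** The plan recognises the pairing for the ratio and then drops the distinction for the detection percentages. An analyst who follows the word chi2 literally would set 10 early results against 10 delayed results as if they came from 20 different patients. That calculation sees only the two totals, so information on who gained and who lost a positive reading is discarded. On a lesion basis it also treats several lesions in one heart as independent observations.

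Sub-Aim 1, which asks whether early imaging detects lesions about as well as delayed imaging, is at stake. A non-significant result from a weak test on 10 patients could be read as showing similarity. The instruction to run the comparison in both groups adds an analysis for which no early control images are described.

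**Working it through.** The documents give no power or effect-size figure for this comparison, so there is none to reproduce. The one count that can be checked agrees: 10 + 20 = 30 patients.

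**Inputs.** From the documents: about 10 pairs and a 0.05 threshold (sidedness is not stated; two-sided assumed). Assumed, because the documents give none: detection rates and the within-patient correlation φ.

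**Formulas.** With early rate p1 and delayed rate p2, P(positive at both) = p1·p2 + φ·√[p1(1−p1)·p2(1−p2)]; the other three cells follow by subtraction. Let b be patients gained at 24 h, c patients lost, and p̄ the pooled rate.

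- Ordinary (Pearson) chi2: (p2−p1)² / [p̄(1−p̄)·2/n], using observed rates.
- Uncorrected McNemar: (b−c)² / (b+c).

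Rejection probabilities come from exact enumeration of all 286 possible paired tables at n = 10.

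**One table by hand.** Early 4/10, delayed 8/10, 4 gained, 0 lost. Pearson: 0.4² / (0.6 × 0.4 × 0.2) = 0.16/0.048 = 3.33, p = 0.068. McNemar: 4²/4 = 4, p = 0.046. The same data fall on either side of 0.05.

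**Size and power at n = 10.** For 50% versus 80% at φ = 0.5, the cells are both 0.40 + 0.5 × 0.5 × 0.4 = 0.50, gained 0.30, lost 0, neither 0.20. At φ = 0.3 they are 0.46, 0.34, 0.04 and 0.16.

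| φ | Pearson size, 50% rate | Pearson power | Uncorrected McNemar power | Exact McNemar power |
|---|---|---|---|---|
| 0 | 0.042 | 25% | 27% | 9% |
| 0.3 | 0.016 | 21% | 33% | 7% |
| 0.5 | 0.005 | 18% | 35% | 5% |

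**Dependence on n.** Ten is only the expected number. At φ = 0, the largest Pearson size over a grid of rates is 0.077 at n = 8, 0.057 at 9, 0.042 at 10, 0.053 at 11 and 0.076 at 13. The largest size of uncorrected McNemar is 0.070 at n = 8, 0.054 at 9, 0.053 at 10 and 0.065 at 11.

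**Which way verdicts differ at n = 10.** Pearson and uncorrected McNemar disagree in 24 of 286 tables: 14 are significant only by Pearson, 10 only by McNemar. All 14 Pearson-only tables have a negative observed correlation (−0.22 to −1.0). For 50% versus 80%, the chance of a Pearson-only verdict is 4.6%, 1.3% and 0.0% at φ = 0, 0.3 and 0.5.

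**Precision.** The 95% score interval for the paired difference, in points: no patient changes, −28 to +28 (here the limit is z²/(n+z²) = 3.84/13.84 = 0.278); one change each way, −34 to +34; 4 gained and 0 lost, 1 to 69.

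**Lesions (illustration only, before clustering).** Suppose 6 are seen at both times, 8 gained and 2 lost. Pearson p is 0.022 with no unseen lesions in the denominator (8/16 versus 14/16), 0.064 with 5 added (8/21 versus 14/21) and 0.092 with 10 added (8/26 versus 14/26). McNemar is 0.058 throughout, but neither test allows for several lesions per patient.

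**Groups.** The Table 1 controls are described with one imaging time, 24 h. Taking the groups as OctreoScan and DOTATATE does not help: the outcome is abnormal OctreoScan, and DOTATATE has one acquisition per injection, after 60 minutes. The DOTATATE interpretation text mentions early and delayed datasets, but no such pair appears in its imaging protocol. The optional second scan follows a new injection, for treatment follow-up.

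**The case against.** McNemar's test is itself a chi-square test, so the plan may intend the paired form. This stands: a reader might infer that the sponsor has chosen an unpaired test, but the text shows only that the form is unspecified.

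No test makes 10 patients in a declared pilot confirmatory, and the ordinary chi2 has more power than exact McNemar (18% against 5% at φ = 0.5). Both are true. They argue for an interval as the main result, not for leaving the test open.

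Three stronger readings are tempting, and the evidence does not carry them:

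- *The ordinary chi2 is always conservative here.* At zero correlation this holds at n = 10 but at no other n from 6 to 15, and 10 is only an expectation.
- *It will produce spurious findings.* Early 3/10 and delayed 8/10 always gives Pearson p = 0.025, while McNemar gives 0.096 with 7 gained and 2 lost. But that table has a correlation of −0.76: early-positive patients would tend to be delayed-negative after the same injection, which is unlikely.
- *The secondary endpoint is compromised.* It is worded as differences in uptake, and the ratio already has a paired t-test.

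The lesion denominator is mainly a missing detail. It may be in the variable attachments, which are not available here. No single choice is clearly right; counting only lesions seen at one or both times removes those seen at neither. Nor does the plan say that early control images do not exist, only that 24 h images were acquired.

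**Conclusion.** The point holds in a limited form. The detection percentages are paired, the plan does not name a paired analysis, and an ordinary chi2 would waste the pairing. At n = 10 with assumed correlation 0.3 to 0.5, its size at a 50% rate is about 0.005 to 0.016 and its power for 50% versus 80% is 18 to 21%, against 33 to 35% for uncorrected McNemar. Near zero correlation its size depends on n and can exceed 0.05, up to about 0.077 for n from 6 to 15. These figures rest on assumed rates and correlations.

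The true size of the lesion-level chi2 cannot be stated from the documents. The two-group comparison cannot be carried out as described. The consequence is limited to the detection rates for Sub-Aim 1 in a pilot; the primary endpoint and the paired t-test on the ratio are unaffected.

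**What to change.** In both places in Statistical methods where early and delayed percentages are compared:

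1. Replace chi2 with the paired difference in detection rate and its 95% score interval, and report the gained and lost counts.
2. If a p value is wanted, name uncorrected McNemar, which agrees with the score interval. State that its size can be modestly above 5% (at most 0.053 at n = 10, about 0.07 at n = 8) and that exact McNemar has less power.
3. Report lesion results descriptively, grouped by patient, without an ordinary chi2 p value. State the denominator, chosen by the sponsor from those its recorded data support.
4. Restrict the comparison to the OctreoScan patients and delete the words extending it to both groups.
5. Judge similarity in Sub-Aim 1 from the interval, not from a non-significant test.

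The cost is a few lines of text and no new data. The downside is an openly imprecise result: even if none of 10 patients changes, the interval runs from about −28 to +28 points.

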- a. higher contrast and spatial resolution of PET/CT for detection of small lesions, which we think will result in improved sensitivity as compared to indium-111 pentetrotide SPECT;
- b. a nearly 75% reduction in the whole body effective radiation dose to patients from a single administration of gallium-68 dotatate (from 16.4 mSv for Octreoscan to 4.3 with Dotatate);
- c. convenience for patients and practical to perform. The entire gallium-68 dotatate PET imaging procedure takes ~2 hours in a single visit, compared to ~24 hours over 2 visits for octreoscan imaging.

II. SPECIFIC AIMS

Aim 1

To investigate if patients with clinically suspected cardiac sarcoidosis exhibit a myocardial OctreoScan or DOTATATE signal high enough (heart-to-blood pool ratio ≥ 2.0) to be visually detected compared to a control group of individuals (expected heart-to-blood pool ratio of ~ 1.0).

Sub-Aim1

To evaluate whether 4-hour (early) compared to 24-hour (delayed) post-OctreoScan injection imaging yields similar lesion detection performance.

Sub-Aim2

To correlate localization and number of increased radiotracer foci between FDG-PET and OctreoScan or between FDG-PET and DOTATATE studies.

Sub-Aim3

To explore the effect of treatment on DOTATATE activity in the heart on follow-up scans

III. SUBJECT SELECTION

We will enroll 30 adult subjects meeting the following inclusion/exclusion criteria.

a. Inclusion Criteria for initial study

- Individuals aged 18 or older

- Documentation of biopsy-proven sarcoidosis OR patients with typical findings on FDG PET and MRI without previous biopsy.

- Clinical suspicion of cardiac involvement defined as the presence of any of the following: high-degree A-V nodal block, complete bundle branch block, reduced left or right ventricular systolic function, any cardiac arrhythmia, and/or unexplained chest pain, dyspnea or syncope

- PET/CT imaging demonstrating abnormal myocardial FDG uptake consistent with active inflammatory myocardium.

b. Exclusion Criteria for initial study

-Initiation of steroids or any other immunosuppressive medication(s) following the completion of FDG-PET, as these medications, in theory, may subsequently suppress OctreoScan or DOTATATE uptake in the heart.

- Patients with history of neuroendocrine tumors (specially insulinomas)
- Patients taking the medication Octreotide
- Patients on total parenteral nutrition (TPN)
- Women who are pregnant or breastfeeding

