2. Semi-quantitative assessment of OctreoScan cardiac uptake: A heart to blood pool background ratio will be calculated using a circular region of interests (ROI) applied to each focus of increased radiotracer uptake visualized in the left ventricle on the transverse and/or coronal tomographic slice of the fused SPECT/CT images. A background ROI of the same size will be applied to the blood pool in the left ventricular cavity. In addition, the relative myocardial contrast will be assessed with measurement of myocardial uptake in ROIs positioned in: 1) interventricular septum 2) lateral wall 3) anterior wall and 4) inferior wall. ROI placement will be confirmed via image fusion with the CT portion from the SPECT/CT study (similar to Figure 2). This qualitative and semiquantitative approach will be performed in both early and delayed datasets by 2 separate nuclear medicine physicians.

Image Interpretation for DOTATATE:

DOTATATE uptake in the heart will be assessed both qualitative and semi-quantitatively.

1. Qualitative Assessment of OctreoScan cardiac uptake: Two board-certified nuclear medicine physicians will review the limited whole body and cardiac PET/CT images independently of each other and grade each image set based on DOTATATE uptake in the heart as: 1) negative, 2) borderline positive or 3) definitely positive. In this latter case, the number and location (relative to the left ventricular wall position) of positive lesions will be recorded.

2. Quantitative assessment of DOTATATE cardiac uptake: The axial PET image slice with maximum cardiac uptake will be selected. A standardized 15 mm circular region will be placed over each myocardial wall area with the peak activity. ROI placement will be confirmed via image fusion with the CT portion from the PET/CT study. Each ROI will be used to derive maximum (SUVmax) and mean standardized uptake values (SUVmean). A background ROI of the same size will be applied to the blood pool in the left ventricular cavity, and similarly, SUVmax and SUVmean will be derived to serve as reference. Then, signal-to-background ratios will be calculated.

This qualitative and semi-quantitative approach will be performed in both early and delayed datasets by 2 separate nuclear medicine physicians.

BIOSTATISTICAL ANALYSIS

a. Specific data variables being collected for the study

Please see excel attachments

b. Study endpoints

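### The lesion-basis chi2 for 4 h versus 24 h OctreoScan ignores both clustering within patients and pairing of the two time points, so its P value is not valid in either direction

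*Combined protocol and SAP*

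**What the plan says.** Sub-Aim 1 (section II) is "To evaluate whether 4-hour (early) compared to 24-hour (delayed) post-OctreoScan injection imaging yields similar lesion detection performance". The related endpoint in the biostatistics section is "Secondary Endpoint: Differences in OctreoScan uptake at 4 hours vs. 24 hours post-radiotracer injection".

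Under Statistical methods, the evaluation of early versus delayed imaging reads "We will employ chi2 to compare if percentage of patients with abnormal OctreoScan varies significantly both on a patient- as well as lesion-basis". Nearly the same sentence closes the paragraph before it. The threshold is general: "A P value <0.05 will be considered statistically significant for all calculations".

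Several foci per patient are allowed for. Under Image Interpretation for OctreoScan (section V.d), when an image set is graded definitely positive, "the number and location (relative to the left ventricular wall position) of positive lesions will be recorded". The ratio measurement uses a region "applied to each focus of increased radiotracer uptake visualized in the left ventricle".

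On numbers, section V.a says "We expect imaging 10 patients with OctreoScan and 20 patients with DOTATATE". Only the OctreoScan patients have both an early and a delayed scan.

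The plan names a paired method for the continuous heart-to-blood-pool ratio (a paired t-test). It names no paired or clustered method for lesion detection.

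**The concern.** A 2x2 chi2 of lesions (early or delayed, by seen or not seen) needs every entry to be an independent observation. Two features break this.

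- **Clustering.** Foci in one heart share tracer kinetics and blood-pool clearance between 4 h and 24 h, and the registration of each scan, so they may appear or disappear together. The recording rule adds to this. Lesions are listed only for image sets graded definitely positive, so a patient graded borderline at 4 h and definitely positive at 24 h goes from no recorded foci to all of them at once.
- **Pairing.** The early and delayed rows contain the same foci. An unpaired chi2 ignores this.

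The first can make the test anti-conservative and the second can make it conservative. At stake is the answer to Sub-Aim 1. The investigators already expect delayed imaging to detect lesions better, and a significant lesion-basis P value would look like confirmation even if one or two patients produced it and the patient-basis result showed nothing.

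**Working it through.** The plan gives no sample-size calculation, foci per patient or detection rate for this comparison, so there is no stated figure to reproduce.

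**Inputs from the protocol:** about 10 OctreoScan patients (V.a); P<0.05 and chi2 (Statistical methods); more than one focus per patient possible (V.d). **Assumed:** number of foci, detection rates, and how far foci in one patient change together.

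**1. How few foci decide the lesion-basis test.** Let L foci all be seen at 24 h and d of them be missed at 4 h. The rows are (L−d, d) and (L, 0), and Pearson chi2 reduces to 2Ld/(2L−d). The critical value is 3.84. With d = 4:

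| L | chi2 | p |
|---|---|---|
| 10 | 80/16 = 5.00 | 0.025 |
| 20 | 160/36 = 4.44 | 0.035 |
| 30 | 240/56 = 4.29 | 0.038 |
| 40 | 320/76 = 4.21 | 0.040 |

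Four foci can be one patient with four or two patients with two each. Three foci do not suffice: at L = 10, 60/17 = 3.53. With the Yates correction or Fisher's exact test, five or six foci are needed. If 24 h imaging sees only 50% to 90% of foci, Pearson needs from 5 (L = 10) up to 9 (L = 40).

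**2. The same patients on a patient basis.** With k discordant patients all in one direction, exact McNemar p = 2 × 0.5^k, capped at 1:

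- k = 1: p = 1.0
- k = 2: p = 0.50 (Pearson for 8/10 v 10/10 gives 0.14)
- k = 5: p = 0.0625
- k = 6: p = 0.031

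**3. An illustration.** Take 30 foci, six of them in one patient and seen only at 24 h, and the other 24 seen at both times. Then 24/30 v 30/30 gives chi2 = 2×30×6/(60−6) = 6.67, p = 0.0098 (Yates 0.031, Fisher 0.024). Lesion-level exact McNemar (0 v 6) gives p = 0.031. One patient produces all of it.

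**4. Simulated type I error of the chi2 with no average time effect.** The model has 10 patients, foci per patient 1 + Poisson with mean 3, mean logit 1, patient SD 1 on the logit scale, and a patient-by-time effect of varying SD:

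| Persistent lesion effect | Patient-by-time SD | Type I error |
|---|---|---|
| none | 0 to 0.5 | about 0.04 to 0.05 |
| none | 1.5 to 5 | about 0.12 to 0.25 |
| SD 2 | 0 to 1.5 | about 0.01 to 0.05 |
| SD 2 | 3 to 5 | about 0.15 to 0.22 |

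A starker model lets 20% of patients switch all their foci together, in a random direction. At a mean of 3 foci the chi2 rejects 0.34 of the time if all other foci are seen at both scans, and 0.12 if other foci are seen 70% of the time. At a mean of 1.5 foci in the latter setting it rejects 0.04. If foci in those patients switch independently and the rest are seen at both scans, the rate is about 0.03 to 0.06 over means of 1.5 to 4 foci.

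**5. Pairing alone is not the cure.** Lesion-level McNemar rejects 0.19 and 0.18 of the time in the two clustered settings with a mean of 3 foci.

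**The case against.** A reader might infer that the lesion-basis P value is always too optimistic. The documents do not support that. Ignoring the pairing pulls the other way, and step 4 shows error at or below 5% when shared change is weak, when lesions differ persistently in visibility, or when patients have few foci. Nothing in the protocol says which setting applies.

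The mechanism is also only partly established. Body habitus and reader are largely common to both scans and largely cancel in the contrast. The preliminary data attribute regional differences to liver and spleen scatter, which need not move all foci together.

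The six-focus illustration is extreme. If lesions were tallied by the four left ventricular walls named in V.d, which the plan does not state, one patient could contribute at most four. With 30 foci Pearson would still give p = 0.038, but lesion-level McNemar would give 0.125.

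Finally, this is a pilot, the test serves a sub-aim, the uptake endpoint has its own paired t-test, and the patient-basis comparison would sit beside the lesion-basis one, so a discrepancy would be visible.

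All of this limits the size and certainty of the point. It does not remove it: the plan still attaches a significance test to a unit that is not independent.

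**Conclusion.** The point holds in this form: the planned lesion-basis chi2 uses the wrong unit and ignores pairing, so its P value cannot be relied on in either direction. That one or two of about 10 patients *can* decide the result is arithmetic, given full detection at 24 h; with incomplete detection more foci are needed. The error rates, from about 0.01 up to about 0.25 in the logit model, depend on assumed foci counts and correlation.

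Two further inferences would go too far. The primary endpoint, abnormal uptake in patients, does not rest on this test. And the FDG-PET comparison of number and location of foci has no named test, so there is no chi2 there to call wrong.

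The change should be made before analysis. It is a matter for Sub-Aim 1 and does not threaten the study's main question.

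**What to change.** Replace the lesion-basis chi2 with one value per patient: the number of left ventricular foci (or fixed walls) positive at 24 h minus the number positive at 4 h. Count over a prespecified set matched by wall location. Test these values with an exact sign-flip or signed-rank test. Report pooled lesion percentages descriptively, or with a bootstrap interval that resamples patients.

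The text must also define what is counted, because it now speaks of a percentage of patients on a lesion basis and records lesions only for definitely positive image sets. It should say how borderline sets enter and how the two readers' counts are combined.

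Any lesion-count comparison with FDG-PET should likewise use the patient as the unit.

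The cost is a few sentences and no extra patients or scans. The downside is a less favourable lesion-basis result: p<0.05 needs at least six patients changing in the same direction with none opposite (2 × 0.5^6 = 0.031; five give 0.0625). With about 10 patients, a descriptive report may be the more realistic choice.
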